## 5.2 AEs coding/grading

The MedDRA version which will be available at the time of database lock, will be used for the coding purpose of the adverse events.

## 5.3 Search criteria for AE of special interest

The Adverse events of special interest (AESIs) based on MedDRA terms are defined in the Case Retrieval Strategy (eCRS). To select the corresponding records from SAS dataset ECRS in Novartis computing environment, use

- Compound name (DRGNAM)="KJX839",
- Compound indication (DRGINDC)="Hypercholesterolemia",
- Records with MDRAVER = 25.0

| Novartis | Confidential | Page 30 of 37           |
|----------|--------------|-------------------------|
| SAP      |              | Study No. CKJX839A1GB01 |

Safety topics flagged in the eCRS using the safety flag (PSURFL =YES) will be filtered and further safety topics mentioned in section 2.7.1.1 will be considered for analyses.

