Variable (or endpoint)	The variable (or endpoint) to be obtained for each participant that is required to address the clinical question. The specification of the variable might include whether the participant experiences an intercurrent event.
Withdrawal of study consent (WoC)	Withdrawal of consent from the study occurs only when a participant does not want to participate in the study any longer and does not allow any further collection of personal data

Amendment 2

Amendment rationale

The study CKJX839A1GB01 was initiated in July 2021 with the first patient enrolled on 07 July 2021. As of 15th July 2022, 900 patients have been randomised.

The main purpose of the amendment is to:

- a. Updated the definition of investigational treatment and intercurrent events
- b. Corrected typographical errors some of which had been notified to the ethics committee previously
- c. Corrected the use of the word placebo to standard of care + behavioural support
- d. Confirmed the inclisiran group is inclisiran (+/- behavioural support)
- e. Confirmed that if questionnaires are not returned they will be followed up twice at 2weekly intervals
- f. Confirmed that patients will be monitored for safety events for 30 days after their EOS visit and not administration of study treatment
- g. Confirmed that the data analysis in the protocol summary will be from baseline to Day 270 and not Day 90, this now matches section 12.4.1

Changes to the protocol

The changes made to the protocol, and sections affected are listed below

Section	Changes made
Glossary of terms	Update to investigational drug/ treatment and intercurrent events
Amendment 1 - changes to the protocol - exclusion criteria	Key exclusion criteria for triglycerides updated
Amendment 1 - changes to the protocol - section 5.2	Exclusion criteria for triglycerides updated
Amendment 1 - changes to the protocol - section 6.1	Corrected that patients do not need to wait 15 mins after receiving the Inclisiran dose at Day 1
Protocol summary – treatment of interest	Updated ratio to confirm this is 1:1:1
Protocol summary – data analysis	Corrected inclisiran and placebo to inclisiran (+/- behavioural support) and standard of care + behavioural support and confirmed we are looking at changes from baseline to Day 270

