10.2 Reporting requirements for adverse events

In this study, only SAEs will be detected, documented and reported. AEs leading to treatment discontinuation will be documented.

- The investigator or delegate has the responsibility for managing the safety of individual participants and identifying and reporting events that meet the definition of AE leading to treatment discontinuation, and SAEs.
- Novartis qualified medical personnel will be readily available to advise on trial related medical questions or problems.
- NWEH's ConneXon trials platform will be utilised for remote safety monitoring. Using this technology all SAEs will be alerted to the study team. SAEs will be reported to the sponsor within 24 hours of awareness.
- AEs also may be detected when they are volunteered by participants during or between visits or other assessments such as when the patient reported outcomes questionnaires (CSQ-8, PAM (CSQ-8, PAM)) are returned to the study team (see 16.2 Appendix 2: The CSQ-8 PROMs Questionnaire, 16.3 Appendix 3: The PAM PROMs Questionnaire and 16.4 Appendix 4:).

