#### 2.7.1.1 Adverse events of special interest / grouping of AEs

Adverse event of special interest (AESI): The number and percentage of participants who reported TEAEs of special interest will be summarized by PT, treatment group. PTs will be sorted in descending order of frequency in the total column. If a participant reported more than one adverse event with the same PT, the AE will be counted only once. If a participant reported more than one AE within the same AESI, the participant will be counted only once at that AESI. Listing of participants with adverse event of special interest will be provided.

The Compound Case Retrieval Strategy (CRS) will be used to determine the MedDRA search criteria to be used to identify events of special interest.

Adverse event of special interest will include the following:

- Hepatotoxicity (Hepatic events)
- New onset or worsening of diabetis mellitus

For search criteria of AE of special interest, refer to Appendix 5.3.

| Novartis | Confidential | Page 24 of 37           |
|----------|--------------|-------------------------|
| SAP      |              | Study No. CKJX839A1GB01 |

The most recent list of adverse events of special interest at the time of database lock will be used. CRS listing will be provided.

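### SAP 5.3 fixes the AESI search at MedDRA 25.0, against the database-lock rules in SAP 5.2 and 2.7.1.1; some events could drop out of the AESI summary if lock uses a later version

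*SAP*

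**What the plan says.** Three places in the SAP govern the AESI output.

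- SAP 5.2 sets the coding dictionary: "The MedDRA version which will be available at the time of database lock, will be used for the coding purpose of the adverse events". It gives no version number.
- SAP 2.7.1.1 names two AESI topics, hepatotoxicity and new or worsening diabetes. On the source of the search terms it says "The Compound Case Retrieval Strategy (CRS) will be used to determine the MedDRA search criteria", and on timing it says "The most recent list of adverse events of special interest at the time of database lock will be used". For the search itself it sends the reader to SAP 5.3.
- SAP 5.3 is the programming instruction. It names the dataset and the filters for compound and indication, and then adds "Records with MDRAVER = 25.0".

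The pool of events is narrow. Protocol 10.2 states "In this study, only SAEs will be detected, documented and reported", and adds that AEs which end treatment are documented.

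**The concern.** Two of the rules move with database lock and the third is a fixed number. A search list built for one MedDRA version and applied to events coded in another can fail to recognise a term that was added or changed in between.

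The AESI table is the SAP's grouped view of hepatic and diabetes events. Because only serious events and events that end treatment are collected, its counts are likely to be low, and the loss of even one event could be noticeable there. What is at stake is the completeness of that one summary. The underlying data and the efficacy analyses are not in question.

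**Working it through.** The plan states no figure for this point, so there is none to reproduce. The check compares the three rules and then asks whether the documents fix the version at lock.

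**Step 1. The rules side by side**

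| Place | What it governs | Version |
|---|---|---|
| SAP 5.2 | Coding of events | Current at lock, no number |
| SAP 2.7.1.1 | AESI list | Latest at lock |
| SAP 5.3 | Records selected for the search | 25.0, fixed |

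If the version at lock is 25.0, all three can be followed. If it is later, 5.3 cannot be followed together with 5.2 and 2.7.1.1 without mixing versions. No section says that 25.0 will be the lock version, that the number in 5.3 will be refreshed, or which section takes precedence.

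**Step 2. What the documents say about timing**

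Inputs:
- Protocol, Amendment 2 rationale: "As of 15th July 2022, 900 patients have been randomised".
- SAP Table 2-1: the End of Study window closes on Day 284.
- Protocol 10.3.3: SAEs are reported for 30 days after the End of Study visit.
- Assumptions: the last patient was randomised on 15 July 2022, and Day 1 fell 0 to 14 days later.

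Calendar date of Day d = date of Day 1 + (d − 1) days.

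| Milestone | Day 1 = 15 July 2022 | Day 1 = 29 July 2022 |
|---|---|---|
| Day 270 (+269) | 10 April 2023 | 24 April 2023 |
| Day 284 (+283) | 24 April 2023 | 8 May 2023 |
| Day 284 plus 30 days (+313) | 24 May 2023 | 7 June 2023 |

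Lock therefore probably falls in spring 2023 or later. The documents give neither the lock date nor the MedDRA version then current, so this arithmetic does not show that the versions will differ.

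**Step 3. What must happen for an event to be lost from the AESI summary**

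All three conditions are needed:
1. The version at lock is later than 25.0.
2. The filter in 5.3 is applied literally, despite 2.7.1.1.
3. A reported hepatic or diabetes event is coded to a term that was added or changed after 25.0, in a way that defeats the match.

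The documents establish none of the three. On the third, SAP 5.3 does not say whether records are matched by term name or by code, so a term that was only renamed might still be found. Terms unchanged since 25.0 would be found in any case. If any one condition fails, the loss is zero. If all hold, it is one event or more, and the documents give no basis for saying how many.

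**The case against.** The strongest reply is that the body of the SAP already has the right rule. Section 2.7.1.1 calls for the latest list at lock, so the number in 5.3 can be read as a parameter that was current when the text was written and would be updated in practice. This stands only in part. Section 2.7.1.1 itself sends the reader to 5.3 for the search, and 5.3 carries no provision for updating. Where the SAP intends later updating it says so: the exclusion table in SAP 5.6 is expressly open to revision until lock. A programmer who follows the document would apply the fixed filter.

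The second reply concerns consequences. A reader might infer that an unmatched event would vanish without trace. The documents do not support that. SAP 2.7.1 plans tables of treatment-emergent events by system organ class and preferred term, a table by standardised MedDRA query, separate summaries of serious events and of events that end treatment, and a listing of all AEs and SAEs. SAP 2.7.1.1 adds a listing of participants with AESIs and a listing of the retrieval strategy. With so restricted a pool, these could be compared by eye. SAP 5.4 also sets notable criteria for liver tests, fasting glucose and HbA1c that do not depend on MedDRA, although the liver tests are presented only as far as the medical record holds them. This reply stands.

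Third, AESIs are not part of the safety analyses in Protocol 12.5.2, and no hypothesis test uses them. That also stands, and it limits the severity.

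**Conclusion.** The contradiction is real and is visible in the text: a fixed version in SAP 5.3 against a version set at lock in 5.2 and 2.7.1.1. It is a minor internal inconsistency.

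Its effect is conditional on the three steps set out in the working. A reader might go further and infer that hepatic and diabetes events are in fact missed, or that the AESI count falls by some stated percentage. Neither follows. The documents do not give the lock version, do not identify any term that changes between versions, and contain no expected AESI count from which a percentage could be formed. The supportable statement is that some events could drop out of the AESI summary. The number is unknown, probably small and possibly zero. The primary endpoint and the key secondary endpoints are unaffected.

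**What to change.** In SAP 5.3, replace the fixed filter with: `MDRAVER = the MedDRA version used to code the study at database lock`. This brings 5.3 into line with 5.2 and 2.7.1.1 and removes any question of which section prevails.

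Add a programmed check that the version used to code the events equals the version of the selected search records, with an error if they differ, and state that version in the study report.

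The cost is one line of SAP text, one program parameter and one short check. No new data are needed, and no other analysis changes.

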#### 5.4 Laboratory parameters derivations

The following table shows the criteria for clinically notable laboratory values. Not all parameters have notable criteria defined:

#### Table 5-1 Clinical notable criteria for selected laboratory tests

| Test             | Notable post-baseline criteria                       |
|------------------|--|
| Glucose, fasting | $\geq$ 5.5 to < 7.0 mmol/L                           |
|                  | $\geq$ 7.0 mmol/L                                    |
| HbA1c            | $\geq$ 5.7 % to < 6.5 % ( $\geq$ 39 mmol/mol to < 48 |
|                  | mmol/mol)  |
|                  | $\geq 6.5 \% (\geq 48 \text{ mmol/mol})$             |

| Table 5-2Notable Liver function test values |
|---|
|---|

| Criterion   |
|---|
| ALT > 3 x the upper limit of normal range (ULN)                                 |
| ALT > 5 x ULN   |
| ALT > 8 x ULN   |
| ALT > 10 x ULN  |
| ALT > 20 x ULN  |
| AST > 3 x ULN   |
| AST > 5 x ULN   |
| AST > 8 x ULN   |
| AST > 10 x ULN  |
| AST > 20 x ULN  |
| ALT or AST > 3 x ULN  |
| ALT or AST > 5 x ULN  |
| ALT or AST > 8 x ULN  |
| ALT or AST > 10 x ULN   |
| ALT or AST > 20 x ULN   |
| Total bilirubin > 2 x ULN   |
| TBL >2xULN & DBL >ULN   |
| TBL >2xULN & DBL >2xULN   |
| ALP > 2 x ULN   |
| ALT or AST > 3 x ULN and total bilirubin > 2 x ULN                              |
| ALT or AST > 5 x ULN and total bilirubin > 2 x ULN                              |
| ALT or AST > 8 x ULN and total bilirubin > 2 x ULN                              |
| ALT or AST > 10 x ULN and total bilirubin > 2 x ULN                             |
| ALT or AST > 20 x ULN and total bilirubin > 2 x ULN                             |
| ALT or AST > 3 x ULN and Total Bilirubin > 2 x ULN and ALP < 2 x ULN (Hy's law) |

ALT = alanine aminotransferase, AST = aspartate aminotransferase, ALP = alkaline phosphatase, DBL = Direct bilirubin

When a criterion contains multiple laboratory parameters, the criterion will only be considered to have been met when all conditions occur within a 3-day window.

The liver function tests are not required as per the assessment schedule of the protocol. This data collected from EMR based on the availability. Whatever data collected will be presented.

| Novartis | Confidential | Page 31 of 37           |
|----------|--------------|-------------------------|
| SAP      |              | Study No. CKJX839A1GB01 |

Normal ranges provided by medical team will be considered for this analysis since reference ranges are not collected in source data.

## 5.5 Statistical models

#### 5.5.1 Multiple Imputation Wash-out model

A multiple imputation washout model will be utilized for the primary efficacy analysis of the percentage change in LDL-C from baseline to Day 270 endpoint. The washout model can be thought of as a control-based PMM that will be used to explore the possibility of missing data being MNAR for subjects who discontinued the study early. For subjects who discontinued the study early, their missing values will be imputed under the assumption that their outcome would be similar to those in the control group with similar background characteristics. For subjects in the inclisiran groups only missing Day 270 values will be imputed.

For subjects whose LDL-C values are undetectable i.e., both baseline and post-baseline due to device sensitivity for a lipid parameter in inclisiran groups will be considered as missing and imputed under MAR assumption.

For subjects in the control group, their missing values over all visits after early termination as well as undetectable values including both baseline and post-baseline due to device sensitivity for a lipid parameter will be imputed based on the missing at random (MAR) assumption.

Multiple imputation will be used to account for uncertainty in the imputation process and results from the imputed datasets will be combined using Rubin's method. Further details are provided below.

For the control group the following variables will be included in a multiple imputation procedure (SAS PROC MI), this assumes missing data are MAR:

- Baseline value of efficacy measurement (continuous)
- Observed value of efficacy measurement at Day 90 (continuous)
- Observed value of efficacy measurement at Day 270 (continuous)

For the subjects in the inclisiran group who completed the doses and with intermittent missing as well as undetectable data, the following variables will be included in a multiple imputation procedure (SAS PROC MI), this assumes missing data are MAR:

- Baseline value of efficacy measurement (continuous)
- Observed value of efficacy measurement at Day 90 (continuous)
- Observed value of efficacy measurement at Day 270 from the inclisiran group (continuous)

For the subjects in the inclisiran groups and with missing data at Day 270 which does not includes undetectable data, the following variables will be included in a multiple imputation procedure (SAS PROC MI), this assumes missing data are MNAR:

• Baseline value of efficacy measurement (continuous)

| Novartis | Confidential | Page 32 of 37           |
|----------|--------------|-------------------------|
| SAP      |              | Study No. CKJX839A1GB01 |

For each undetectable LDL-C value, a range is determined based on Friedewald's formula. Below table will provide example range calculation when

are distributed in different categories.

As a next step, the undetectable LDL-C values are baseline are imputed to create 500 complete sets of baseline LDL-C values. The imputation is performed by fitting a normal distribution to all available baseline LDL-C values including the LDL-C ranges. The imputed values are obtained by sampling from the posterior predictive distribution. As prior distribution for mean and the standard deviation a normal distribution (mean=0, sd=10) and a half-t-distribution (df=3, scale=2.5) are chosen.

To create 500 complete data sets of baseline and post-baseline LDL-C data sets, the following approach is performed for each of the 500 data sets with complete baseline LDL-C data.

- 1. Fit a Bayesian linear mixed model to all available post-baseline LDL-C data including the LDL-C ranges from Day 90 and Day 270.
  - a. The model includes study arm, visit, and baseline LDL-C as well as all interactions as fixed effects.
  - b. The model includes a normally distributed patient-specific random effect and a normally distributed residual error. The variance of the residual error differs by study arm and visit.

| Novartis | Confidential | Page 34 of 37           |
|----------|--------------|-------------------------|
| SAP      |              | Study No. CKJX839A1GB01 |

- 2. For the missing values or undetectable LDL-C values of patient *i* at visit *j* in study arm *k* that are imputed under the MAR assumption, the imputed value is drawn from the posterior predictive distribution of the outcome (i.e., LDL-C) of patient *i* at visit *j* in study arm *k*.
- 3. For the missing values of patient *i* at visit *j* in the inclisiran arm that are imputed under the jump-to-reference assumption, the imputed value is drawn from the posterior predictive distribution of the outcome (i.e., LDL-C) of patient *i* at visit *j* whereas the components (e.g., fixed effects and random effects) of the posterior predictive distribution that are associated with the inclisiran arm are replaced by the corresponding value from the placebo arm.

The above imputation will be carried out using R software.

Each of the 500 complete data sets is analyzed with an ANCOVA as specified for the primary analysis. The resulting point estimates will be combined using Rubin's method.

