#### 2.5.5 Sensitivity analyses

The following sensitivity analyses will be performed for the primary estimand, to assess the robustness of the estimation in the presence of deviations from the assumptions specified in the primary analysis on the FAS only:

| Novartis | Confidential | Page 18 of 37           |
|----------|--------------|-------------------------|
| SAP      |              | Study No. CKJX839A1GB01 |

• Linear mixed-effect model for repeated measures (MMRM) analysis without multiple imputation

Analyses using the MMRM will include fixed effects for treatment, visits, interaction between treatment and visits, baseline LDL-C and interaction between baseline LDL-C and visit. Day 90 and 270 will be included as visit. The Restricted Maximum Likelihood (REML) estimation approach will be used with covariance structure set as "Unstructured". If the model does not converge with unstructured covariance matrix, the compound symmetry covariance matrix will be used in the mixed model.

As a sensitivity analysis, the imputation algorithm will be changed from a regression approach to a multivariate normal model to include in the imputation information that is provided by undetectable LDL-C values. An LDL-C value is undetectable when either

are outside of the limit of detection. Based on the limit of detection and through Friedewald's formula, a range for an LDL-C value can be calculated. In this sensitivity analysis, the LDL-C range is considered in the imputation model. As for the primary analysis, undetectable LDL-C values for either study arm are imputed under a MAR assumption, missing values in the placebo arm are imputed under a MAR assumption, and missing data on Day 270 or after treatment discontinuation in the inclisiran arm are imputed using a wash-out model (i.e., using a jump-to-reference approach).

In the sensitivity analysis, imputed baseline values will be restricted to  $\ge 0.1$  to avoid imputed values close to zero which can lead to numerical instabilities in the analysis of percentage LDL-C change from baseline.

The imputation will be carriedout using in SAS/R as mentioned in Appendix 5.5.2.

The analysis will be carried out using ANCOVA procedure as mentioned in section 2.5.2.

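### The undetectable-data sensitivity analysis draws baseline LDL-C without the participant's own follow-up values or arm, which adds avoidable noise to percentage change

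*SAP*

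**What the plan says.** SAP 2.5.5 announces that, for undetectable LDL-C, "the imputation algorithm will be changed from a regression approach to a multivariate normal model", so that the range implied by Friedewald's formula can be used. It adds that undetectable values in either arm are imputed under missing at random, as in the primary analysis. A floor applies at baseline: "imputed baseline values will be restricted to" at least 0.1, to avoid unstable percentage changes.

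The detail is in the appendix. The contents list and 2.5.5 place it in 5.5.2; in the public text that heading is missing and the passage runs on from 5.5.1. It has two ordered steps:

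- **Baseline.** "The imputation is performed by fitting a normal distribution to all available baseline LDL-C values including the LDL-C ranges". Then: "The imputed values are obtained by sampling from the posterior predictive distribution".
- **Follow-up.** With baseline complete, "the following approach is performed for each of the 500 data sets with complete baseline LDL-C data". The instruction is: "Fit a Bayesian linear mixed model to all available post-baseline LDL-C data including the LDL-C ranges from Day 90 and Day 270". Baseline is a covariate: "The model includes study arm, visit, and baseline LDL-C as well as all interactions as fixed effects".

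No step returns to the baseline draws.

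The primary imputation in SAP 5.5.1 works differently. For the control group, and for inclisiran participants who completed dosing but have intermittent or undetectable values, baseline, Day 90 and Day 270 enter one PROC MI call. The list includes "Observed value of efficacy measurement at Day 90 (continuous").

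**The concern.** A participant's follow-up LDL-C carries information about an unobserved baseline. Imputation under missing at random should condition on what was observed, and here that includes Day 90 and Day 270. Arm matters too, because it tells the model how a given follow-up value relates to baseline. The appendix uses none of this for baseline.

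For an endpoint on the raw scale the loss might be tolerable. Here the endpoint is 100 x (follow-up - baseline) / baseline (SAP 2.1.1), so error in the baseline draw becomes error in the outcome, magnified when the draw is small. The same completed baseline is also the ANCOVA covariate, so the noise weakens the adjustment as well.

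What is at stake is the usefulness of this one sensitivity analysis. Its purpose is to show what the range information does. If it also drops follow-up information, a wider interval or a moved estimate may reflect the cruder baseline step.

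**Working it through.** **1. The plan's own figure.** The documents give no figure for the imputation. The sample size reproduces: 2 x (1.960 + 1.282)^2 / 0.3^2 = 234 per arm, and 234 / 0.8 = 293, consistent with 300. This point does not affect it.

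**2. What conditioning adds.** Take baseline B with SD s, and follow-up Y with slope b on B and residual SD e. The planned draw has SD s before restriction to the range. The conditional draw has variance s^2 - (b s^2)^2 / (b^2 s^2 + e^2). Assume s = 0.9 mmol/L and one follow-up value.

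- Control, correlation 0.6: SD = 0.9 x sqrt(1 - 0.36) = 0.72.
- Inclisiran, b = 0.5, e = 0.55: variance = 0.81 - 0.405^2 / 0.505 = 0.485, so SD = 0.70.

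The conditional draw is also centred on a value consistent with the participant's follow-up. The denominator magnifies errors: with follow-up 1.5 mmol/L, a baseline draw of 1.5 gives 0% change, and a draw at the 0.1 floor gives 100 x (1.5 - 0.1) / 0.1 = 1,400%.

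**3. Simulation with wide ranges.** Assumptions: 300 per arm; baseline mean 2.7, SD 0.8; correlation 0.6; follow-up slope 1.0 (control) and 0.5 (inclisiran); draws restricted to 0.1 up to U; unequal-variance ANCOVA; Rubin's rules; 150 trials of 30 imputations. SE of the treatment difference, baseline-only / joint draw:

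| Undetectable | U = 1.5 | U = 2.0 | U = 2.7 | SE increase |
|---|---|---|---|---|
| 1% | 2.59 / 2.52 | 2.58 / 2.49 | 2.56 / 2.50 | 2.4-3.6% |
| 3% | 2.85 / 2.59 | 2.74 / 2.52 | 2.69 / 2.50 | 7.6-10.0% |
| 5% | 3.11 / 2.71 | 2.94 / 2.58 | 2.84 / 2.54 | 11.8-14.8% |

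The estimate moved by amounts from within simulation error to about 0.8 points. A separate run with range-restricted draws, again with wide ranges reaching near zero, gave SE increases of 2-4%, 6-10% and 11-14%, and a shift of 0.05-0.3 points favouring inclisiran that the conditional draw removed.

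**4. Simulation with other ranges.** Assumptions: 240 evaluable per arm (300 x 0.8); baseline mean 3.0, SD 0.9; 20 imputations; percentage-change SDs close to the planned 30% and 20%.

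| Undetectable | Range | SE, baseline-only / conditional | RMS error of imputed % change |
|---|---|---|---|
| 5% | uninformative | 2.38 / 2.28 (+4%) | 37.9 / 28.9 |
| 15% | uninformative | 2.59 / 2.34 (+11%) | 39.0 / 29.3 |
| 5% | 1.0 mmol/L | 2.27 / 2.27 | 13.0 / 12.2 |
| 15% | 1.0 mmol/L | 2.30 / 2.27 (+1.3%) | 13.4 / 12.8 |
| 15% | 0.5 mmol/L | 2.27 / 2.27 | 6.9 / 6.8 |

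The estimates from the two draws differed by less than 0.2 points throughout. The increases are smaller than in step 3 partly because baselines here never fall below 1.2 mmol/L in the uninformative case, so there are no near-zero denominators.

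**5. Effect on the conclusion.** With the planned SDs and 240 per arm, SE = sqrt(900/240 + 400/240) = 2.33, and 10 / 2.33 - 1.96 = 2.34, a power of about 99%. Even at the largest simulated SE of 3.11, a 10-point difference gives z = 10 / 3.11 = 3.2. An effect of about 50 points, as in the phase III trials (Protocol 1.1.4.1), gives 50 / 3.11 = 16.

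**The case against.** **The appendix does not flatly contradict 2.5.5.** A reader might infer that a multivariate normal model was promised and a univariate one delivered. The documents do not support that. A normal model for baseline followed by a normal model for follow-up given baseline is one way to write a joint normal model. What stands is narrower: drawing an unobserved baseline from that joint model requires conditioning on follow-up, and the appendix does not do so.

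**The imputed percentage change is not a ratio of unrelated numbers.** That too is tempting and too strong. The range comes from the participant's own lipid results, and imputed follow-up is drawn given the completed baseline. The appendix does not say outright that baseline draws are confined to the range, but the simulations assume so and the loss remains when ranges are wide.

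**Wide ranges near zero may be unusual.** With total cholesterol at least 4 and triglycerides below 4.52 mmol/L, Friedewald's formula gives LDL-C above 4 - 4.52/2.2 - HDL = 1.95 - HDL, so a value near 0.1 needs HDL above about 1.85. This carries weight. It does not settle the matter, because Protocol 8.2 takes eligibility cholesterol from the medical record, breaches of either criterion do not exclude a participant from the full analysis set (SAP 5.6), and the 0.1 floor shows that very low baseline draws were expected.

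**The sensitivity analysis already differs from the primary in other ways.** It uses a Bayesian mixed model with variances by arm and visit, so a joint baseline draw would not isolate the effect of the ranges. That is fair. It would remove one unnecessary difference.

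**Conclusion.** The point holds as a modest loss of efficiency and clarity in one sensitivity analysis. The planned baseline draw leaves out observed data that the primary imputation uses, and the endpoint's denominator makes that loss visible.

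The size depends on two things that the visible documents do not give: the share of undetectable baselines and the width of the ranges (the range table and the names of the lipid limits are not in the public text). For wide ranges reaching near zero, the SE increase is about 2-4% at 1% undetectable and 11-15% at 5%, with a shift of a few tenths of a point. For ranges of 1.0 mmol/L or narrower it is about 1% or less. The simulations used 150 trials per setting and the Monte Carlo error of the SE ratios was not calculated, so these are orders of magnitude.

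A reader should not infer that the primary result is at risk. The primary imputation is untouched, the extra noise mainly widens an interval, and the expected effect is many standard errors from zero.

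**What to change.** In SAP 5.5.2, replace the separate baseline step with a draw from the joint normal model, conditional on the participant's range, arm and observed Day 90 and Day 270 values. One way is to treat each undetectable baseline as an interval-censored parameter in the Bayesian model already planned for follow-up, with one baseline mean common to all arms because allocation is random. State explicitly that draws stay within the participant's range.

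Keep the rest of the specification: residual variances by arm and visit, the baseline interactions, the 0.1 floor, and the jump-to-reference rule for missing inclisiran follow-up. Report the number of undetectable baselines by arm and their range widths, so that readers can judge whether the step matters.

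If the two-step approach is kept, reword 2.5.5 to describe it and justify leaving follow-up out of the baseline draw.

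The cost is a SAP wording change, recoding one R model and somewhat longer run time. No new data are needed.
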